^a At the time of discontinuation for the study, an early termination (ET) visit should be conducted, if possible.

- ^b Participants with significant symptoms at the Day 168 EIA will be followed for an additional 4 weeks at the discretion of the Investigator.
- ^c Visits without a specified window are to be conducted relative to the associated scheduled visit. For example, Day 28 will always be the day prior to the Day 29 visit, regardless of where Day 29 falls within the \pm 2-day visit window.
- ^d Screening tests positive for cannabis are not exclusionary.
- ^e To include hematology (CBC with differential and RBC indices), clinical chemistry, coagulation panel, urinalysis, viral serology, HbA_{1c}, and FSH (as indicated). See [Section 10.2](#) for a complete list of parameters.
- ^f Baseline genetic testing for *ALDH2* mutations. Participation is optional; participants who do not wish to undergo genotyping may still participate in the study.
- ^g The Baseline version will be administered at Screening and at subsequent visits the “C-SSRS Since Last Visit” version will be administered. Participants who exhibit signs of Suicidal Ideation or Behavior (SIB) should undergo a risk assessment. All factors contributing to SIB should be evaluated and consideration should be given to discontinuation of study intervention.
- ^h TLFB will be completed for the 2-week period that precedes each study visit, including Screening.
- ⁱ Pregnancy testing required only in female participants. If a urine pregnancy test is positive, confirm with serum pregnancy test. Local laboratory may be used. Female participants must have a negative pregnancy test prior to overnight admission.
- ^j Testing to be performed at the site upon admission. Participants with a positive SARS-CoV-2 test will not be admitted to clinic and will not receive study intervention or undergo EIA. Other assessments not requiring clinic admission (i.e., safety assessments) will be performed. Testing will be performed per site standard processes.
- ^k Study participants are to refrain from drinking alcohol and using cannabis for 24 hours prior to each EIA. Participants with a positive urine-drug or breath-alcohol test will not be admitted to clinic and will not undergo EIA. Participants with a positive urine drug test on Day –1 will be excluded from the study.
- ^l Participants must be fasting for at least 3 hours prior to admission to the clinic.

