- ^m Participants may be discharged from clinic following collection of the 24-hour postdose PK sample. Participants will return to clinic for collection of PK samples at 72 hours postdose on Days 4 and 32.
- ⁿ EIA will be conducted on the first day of the visit once all other assessments for that day have been completed. A total of 10 EIAs will be conducted. The timing of assessments and ethanol administration are detailed in [Table 3](#).
- ^o On dosing days, ECGs will be conducted approximately 30 minutes predose and 15-to-30 minutes postdose. If multiple assessments are due, the order of assessment should be ECG, vitals, PK, and then other assessments; with PK sample collection occurring at the nominal time. At Screening and EOS, one ECG will be performed. Screening ECGs may be repeated one time for determination of eligibility.
- ^p Blood pressure, if out of range at Screening, may be repeated one time for determination of eligibility.
- ^q Blood pressure and pulse rate to be recorded 15 (\pm 5) minutes postdose.
- ^r Height will be measured and recorded at Screening. Weight will be measured and recorded at every visit.
- ^s Sample to be collected prior to ethanol administration.
- ^t Hematology to include complete blood count with differential and RBC indices. See [Section 10.2](#) for a complete list of parameters.
- ^u See [Section 10.2](#) for a complete list of parameters.
- ^v Blood samples for complement testing to be collected predose and 2, 8, and 24 hours postdose on Day 1 and Day 57.
- ^w Blood sample for ADA testing to be drawn at same time as predose PK sample on Day 1.
- ^x Plasma samples for PK analysis to be collected predose and at 1, 2, 4, 6, 8, 24, and 72 hours postdose (exception: no 72-hour PK sample is required at Day 57). A single sample will be collected on Day 168. If multiple assessments are due, the order of testing should be ECG, vitals, PK, and then other assessments, with the PK sampling performed preferably at the nominal time point. A \pm 15-minute window will be allowed for collections at 1, 2, 4, 6, and 8 hours postdose. A \pm 30-minute window will be allowed for collection at 24 hours postdose. A \pm 60-minute window will be allowed for collection at 72 hours postdose.
- ^y Participants to record any symptoms associated with use of alcohol outside of in-clinic EIAs. Diary to be issued at time of discharge from clinic and collected and reviewed upon return to clinic.

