3 INVESTIGATIONAL PLAN

3.1 Overall Study Design and Plan

This is a double-blind, randomized, placebo-controlled study of DCR-AUD to evaluate the safety, tolerability, PK, and PD of repeat doses of DCR-AUD in adult HVs.

Participants will receive 3 injections of study intervention (Day 1, Day 29, and Day 57), and have assessment visits through Week 24. Up to 10 EIAs will be conducted over the 24-week period to characterize the PD of DCR-AUD. For each EIA, participants will consume 4 standard drinks over the course of 80 minutes. Participants will be admitted to the clinic overnight for each EIA. At the discretion of the Investigator, participants who present with increasing positive ethanol reaction symptoms at the Day 169 EIA (flushing, headache, lightheadedness, palpitations, nausea, or vomiting) will be followed for an additional 4 weeks (through Day 197).

Figure 3-1 Study Schematic for DCR AUD-102

- a. DCR-AUD (480 mg) or placebo administered on Days 1, 29, and 57
- b. 4-Week conditional follow-up (CFU) conducted at the discretion of the Investigator in participants experiencing symptoms at the End-of-Study (Week 24) visit.

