3.2.5 Pharmacodynamic Variables

DCR-AUD is designed to selectively reduce ALDH2 activity in the liver and the conversion of acetaldehyde to acetic acid after alcohol consumption. The build-up of acetaldehyde causes unpleasant effects after drinking (e.g., flushing, headache, lightheadedness, palpitations, nausea, or

vomiting). As such, the PD activity of DCR-AUD will be assessed during EIAs via these 6 symptoms, and blood biomarkers (ethanol, acetaldehyde, and acetate) PD parameters to be estimated by Clinical Pharmacology, Modeling and Simulation (CPMS) group are provided in [Table 3-1](#).

Table 3-1 Plasma Pharmacodynamic Parameters

Protocol Parameter	WNL Name	Definition
t_{max}	Tmax	Time corresponding to occurrence of C_{max} (For acetaldehyde, acetate, and alcohol)
C_{max}	Cmax	Maximum observed concentration (in the unit of μM and ng/mL) (For acetaldehyde, acetate, and alcohol)
$C_{maxAbove}$	Cmax_Above_B	Maximum observed concentration that is above the baseline (in the unit of μM and ng/mL) (For acetaldehyde)
baseline	Baseline	Response value just prior to treatment administration
AUC_{Above}	AUC_Above_B	Area under the curve that is above the baseline (for acetaldehyde)
AUC_{Below}	AUC_Below_B	Area under the curve that is below the baseline (for acetate)
AUC_{0-4h}	AUCT	Observed partial area under the curve from time 0 to 4 hours (for acetaldehyde, acetate, and alcohol)
C_{av}	Cav	Average plasma concentration from time zero to 4 hours
PD response change	PD_response_change	Changes in each biomarker level on each EIA day (i.e., D1,14,29,42, 57) compared to the basal level on Day -1
PD response % change	PD_response_%_change	Percent changes in each biomarker level on each EIA day (i.e., D1,14,29,42,57) compared to the basal level on Day -1

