4.12.3 Statistical Analysis of Pharmacokinetic Parameters

We will use a one-way analysis of variance to compare the PK parameters of ALDH2 mutation. If there are 3 or more subjects with ALDH2 mutation, the PK parameters of these subjects as a group will be compared to those without ALDH2 mutation as another group. Otherwise, the PK parameters will be summarized with and without the individual(s) with ALDH2 mutation.

Sample SAS Code:

```
PROC MIXED DATA = DATA1 NOPRINT;
BY PARAMCD;
CLASS MUTATION;
MODEL LN_PK = MUTATION /DDFM = KR;
RUN;
```

WHERE,

PARAMCD :short name of PK parameter

LN_PK; natural log transformed value of PK parameter
MUTATION: Group for the genetic mutation.

4.12.4 Pharmacodynamic Analysis, Concentration, and Parameter TFLs, and Statistical Analysis of Pharmacodynamic Parameters

Pharmacodynamic parameters will be estimated according to the guidelines presented in Table 4-2.

Table 4-2 Pharmacodynamic Parameter and Estimation

Parameter	Guidelines for Derivation
Cmax, tmax,	Obtained directly from the observed concentration-time data
C_{av}	The average concentration from time 0 to time 4 h: $AUC_{0-4\text{ h}}$
$AUC_{0-4\text{ h}}$ -adjusted	The AUC adjusted from zero time to 4 h for Day X: $AUC_{0-4\text{ h}}(\text{Day X}) - AUC_{0-4\text{ h}}(\text{Day -1})$
C_{av} -adjusted	The C_{av} adjusted for Day X is time averaged concentration from zero time to 4 h: $C_{av}(\text{Day X}) - C_{av}(\text{Day -1})$
Cmax-adjusted	The Cmax adjusted for Day X is: $C_{max}(\text{Day X}) - C_{max}(\text{Day -1})$
$AUC_{0-4\text{ h}}$ percent change	Percent change of $AUC_{0-4\text{ h}}$ on Day X as compared to the basal level (Day -1): $((AUC_{0-4\text{ h}}(\text{Day X}) - AUC_{0-4\text{ h}}(\text{Day -1})/\text{day -1})) \times 100$
C_{av} percent change	Percent change of C_{av} on Day X as compared to the basal level (Day -1): $((C_{av}(\text{Day X}) - C_{av}(\text{Day -1})/\text{day -1})) \times 100$
Cmax percent change	Percent change of Cmax on Day X as compared to the basal level (Day -1): $((C_{max}(\text{Day X}) - C_{max}(\text{Day -1})/\text{day -1})) \times 100$

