Record concomitant meds	X	X	X	X	X	X	X	X	X	X	X	X	X

Abbreviations: ADA=antifdrug antibody; AE=adverse event; ALDH2=aldehyde dehydrogenase 2 gene; CBC=complete blood count; CFU=conditional follow-up visit; C-SSRS=Columbia-Suicide Severity Rating Scale; ECG=electrocardiogram; EIA=ethanol interaction assessment; EOS=end of study; ET=early termination; FSH=follicle-stimulating hormone; HbA1c=hemoglobin A1c; ICF=informed consent form; MINI=Mini-International Neuropsychiatric Interview; PEth=phosphatidylethanol; PK=pharmacokinetic; RBC=red blood cell; SAE=serious adverse event; SARS-CoV-2=severe acute respiratory syndrome coronavirus 2; SIB=suicidal ideation or behavior; TLFB=Timeline Follow Back; UA=urinalysis

^a At the time of discontinuation for the study, an early termination (ET) visit should be conducted, if possible.

Project Document Version No.: 2.0, Document Effective Date: 01 Sep 2023

TP-GDO-WW-133-04

Effective Date: 28 Jul 22

Related to: SOP-GDO-WW-019

Developed from TP-BPM-WW-032; related to SOP-BPM-WW-001

Downloaded by [REDACTED] on 06 Sep 2023

Statistical Analysis Plan

- ^b Participants with significant symptoms at the Day 168 EIA will be followed for an additional 4 weeks at the discretion of the Investigator.
- ^c Visits without a specified window are to be conducted relative to the associated scheduled visit. For example, Day 28 will always be the day prior to the Day 29 visit, regardless of where Day 29 falls within the \pm 2-day visit window.
- ^d Screening tests positive for cannabis are not exclusionary.
- ^e To include hematology (CBC with differential and RBC indices), clinical chemistry, coagulation panel, urinalysis, viral serology, HbA_{1c}, and FSH (as indicated). See protocol for a complete list of parameters.
- ^f Baseline genetic testing for *ALDH2* mutations. Participation is optional; participants who do not wish to undergo genotyping may still participate in the study.
- ^g The Baseline version will be administered at Screening and at subsequent visits the “C-SSRS Since Last Visit” version will be administered. Participants who exhibit signs of Suicidal Ideation or Behavior (SIB) should undergo a risk assessment. All factors contributing to SIB should be evaluated and consideration should be given to discontinuation of study intervention.
- ^h TLFB will be completed for the 2-week period that precedes each study visit, including Screening.

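### Several SAP pharmacodynamic definitions contradict the SAP's own EIA schedule and each other: EIA days in Table 3-1, the Delta 3 test count, and the biomarker AUC window and method reference

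*SAP*

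**What the plan says.** **Schedule.** Protocol 1.3, Table 1 footnote n, states "A total of 10 EIAs will be conducted" and "EIA will be conducted on the first day of the visit once all other assessments for that day have been completed". Footnote c adds that "Day 28 will always be the day prior to the Day 29 visit". SAP 6.1 carries the same schedule. SAP 3.1 gives the dosing days: "DCR-AUD (480 mg) or placebo administered on Days 1, 29, and 57".

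**EIA days.** In SAP 3.2.5, Table 3-1, the first PD response row reads "Changes in each biomarker level on each EIA day (i.e., D1,14,29,42, 57) compared to the basal level on Day -1". The percent-change row lists the same five days. Table 4-2 gives no list and uses an open day, for example "Percent change of Cmax on Day X as compared to the basal level (Day -1".

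**Delta 3.** SAP 4.12.1.2.2 defines it as the participant's highest Delta 1 across all tests after dosing, and puts the number of tests at 6.

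**AUC window and method.** SAP 4.12.1.2.1 tabulates AUC0-2.5h and then plots AUC0-4h. Table 3-1, Table 4-2 and section 4.12.5 use only 0 to 4 h. The same paragraph of 4.12.1.2.1 takes its method from Section 4.10, whose whole content is that it is not applicable. Section 4.12.2 sets out noncompartmental rules for PK, Table 4-2 gives PD derivations, and 4.12.5 says that PD parameters come from a drug effect model.

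**Last EIA.** SAP 3.1 refers to "participants who present with increasing positive ethanol reaction symptoms at the Day 169 EIA". SAP Table 6-1 footnote b says "Participants with significant symptoms at the Day 168 EIA will be followed for an additional 4 weeks".

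**The concern.** These are operative analysis rules, not background text. Read literally, Table 3-1 asks for biomarker changes on three days when no EIA is scheduled and names no EIA after the third dose. Delta 3 has a count that cannot be right. One section tabulates a different AUC from the one it plots, and its method reference leads nowhere.

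The late EIAs are where agreement matters most. Protocol 4.2 argues that an effect may need repeat dosing and several months to appear. Delta 3 summarises the 6-symptom score, whose change protocol 9.4.3 names as the principal secondary endpoint. If the plan leaves these points to the programmer, the set of tests, the AUC window and the method get settled outside the plan, possibly with data in view.

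**Working it through.** **1. Reproduce the stated number of EIAs.** Each EIA falls on the first day of its visit.
- Dosing and end-of-study visits (protocol Table 1, SAP Table 6-1): Days -1, 28, 56, 168, which is 4.
- Non-dosing visits (protocol Table 2, SAP Table 6-2): Weeks 2, 6, 10, 12, 16, 20, which is 6. Days 14, 42, 70 and 84 are printed. Days 112 and 140 are derived as 16 × 7 and 20 × 7, because those column labels are not legible in the text used here.
- Total: 4 + 6 = 10, matching the stated 10.
- Post-dose: 10 − 1 = 9 (Days 14, 28, 42, 56, 70, 84, 112, 140, 168).
- After the third dose on Day 57: Days 70, 84, 112, 140, 168, which is 5.

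**2. Compare with Table 3-1 (Days 1, 14, 29, 42, 57).**
- Literal reading: 14 and 42 are EIA days, and 1, 29 and 57 are dosing days. So 2 of 5 listed days match, and 9 − 2 = 7 post-dose EIAs are not named.
- Lenient reading, taking 1, 29 and 57 as labels for the EIAs the day before dosing (Days -1, 28, 56): 4 of 9 post-dose EIAs are named and 9 − 4 = 5 are not.
- On either reading, 0 of the 5 EIAs after the third dose are named.

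**3. Delta 3.** Scheduled 9, stated 6, difference 3. Six happens to equal the number of non-dosing visits, but the text says all tests after dosing, which also takes in Days 28, 56 and 168. A maximum over any 6 of the 9 tests can only equal or fall below the maximum over all 9.

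**4. AUC window.** Ethanol is taken over 80 minutes.
- 0 to 2.5 h ends 150 − 80 = 70 minutes after intake ends.
- 0 to 4 h ends 240 − 80 = 160 minutes after intake ends.
- The shorter window leaves out 1.5 of 4 h, or 37.5% of the time.

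The documents give no concentrations, so the effect on the AUC itself can only be illustrated with assumed profiles:
- Flat: 2.5 / 4 = 0.625 of AUC0-4h.
- Linear rise to a peak of 1 at 1.5 h, then linear fall to half at 4 h: (0.75 + 0.90) / (0.75 + 1.875) = 0.629.
- Same rise, then linear fall to zero at 4 h: (0.75 + 0.80) / (0.75 + 1.25) = 0.775.

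Under these assumptions the two AUCs are not interchangeable.

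**5. Method.** Section 4.10 contains none. The three candidates (4.12.2, Table 4-2, 4.12.5) are not tied together. Table 4-2 also equates the average concentration C_av with AUC0-4h, whereas an average over 4 h is AUC0-4h / 4. As printed, C_av and its Day -1 difference are 4 times too large. The percent change is unaffected, because the factor cancels.

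**The case against.** The strongest defence is that nothing is lost. The governing words in Table 3-1 are that the change is taken on each EIA day, and the list is only a parenthesis. The SAP uses the same abbreviation loosely elsewhere: Table 3-2 illustrates a fixed-time AUC with 24 and 48 hours, although no 48-hour PK sample is scheduled. Day X in Table 4-2 covers every EIA, and sections 4.12.4, 4.12.5, 4.12.1.1 and 4.12.1.2.1 call for outputs by EIA day or at each EIA. No EIA biomarker samples are scheduled on dosing days, so a literal programming of the list would fail visibly.

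Most of this stands. A reader might infer that late biomarker results would be dropped, and the documents do not support that. A reader might also infer that Delta 3 has no defined set of tests. It does, namely all tests after dosing, and only the count is wrong. The SAP's allowance of up to 10 EIAs covers missed tests but does not explain a fixed 6.

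On the AUC, 2.5 h appears once against several uses of 4 h, and 4.12.5 already calls for summaries of the biomarker parameters, so AUC0-4h should be reported anyway. That shows which window to keep, but the contradictory instruction remains. The noncompartmental rules and the drug effect model may be compatible, but the SAP does not say how.

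**Conclusion.** The point holds as an internal inconsistency to correct. Table 3-1 lists three dosing days among five and names none of the five EIAs after the third dose. Delta 3 states 6 tests where 9 are scheduled. One table uses AUC0-2.5h against AUC0-4h elsewhere, and its method reference is empty. These are counts of labels, tests and minutes, not of lost analyses. The effect on any result cannot be computed from the documents, and the AUC shares above rest on assumed profiles.

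Only secondary PD outputs are touched, in a study that protocol 9.1 calls descriptive. The primary safety endpoints are not affected.

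Two assumptions apply. The first-day rule is stated only for the Table 1 visits and is carried over to the non-dosing visits; the count of 10 EIAs does not depend on it. The C_av formula is taken as it reads in the text, and since a lost denominator is possible, it should be checked in the original.

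Three side notes do not carry the conclusion:
- The last EIA is called both Day 168 and Day 169 in the protocol (Day 169 in 1.1.3 and 4.4; Day 168 in 1.3, 4.1 and 8.6.1.4) as well as in the SAP.
- SAP 4.12.1.1 counts symptom times from study drug administration, while Table 6-3 sets time 0 just before the first sip of ethanol.
- Protocol 8.6.1 and SAP 4.12.1.1 differ on when a missed EIA may be made up and who decides. That is a conduct inconsistency, not an analysis error.

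**What to change.** 1. **Table 3-1, both PD response rows:** replace the day list with each post-dose EIA in the Schedule of Activities (9 scheduled), as for Day X in Table 4-2.
2. **Delta 3 (4.12.1.2.2):** replace the count of 6 with all post-dose EIAs performed (up to 9).
3. **Section 4.12.1.2.1:** use AUC0-4h in the summary table. Replace the reference to Section 4.10 with one stated method that reconciles 4.12.2, Table 4-2 and the drug effect model sentence in 4.12.5. If Table 4-2 is cited, give C_av as AUC0-4h divided by 4 h.
4. **Side notes:** count the 4.12.1.1 symptom times from the first sip of ethanol, as in Table 6-3, after checking them against the eCRF. Reconcile the Day 168/169 label across both documents, and the make-up EIA wording between protocol 8.6.1 and SAP 4.12.1.1.

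**Cost:** items 1 to 3 are SAP wording, or an entry in the Statistical Method Modification Form that the SAP provides for changes after finalization. The day label and the make-up wording need both documents aligned. No new data are needed.

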3.2.6 Immunogenicity Variables

Immunogenicity testing (anti-drug DCR-AUD antibodies) using designated serum samples from each participant is planned to be conducted.

The ADA samples collected in this study will be stored and analyzed in the future

3.2.7 Pharmacokinetic Variables

Pharmacokinetic concentration data will be obtained at time point(s) described in the protocol version 2.0 as follows:

PK concentrations of DCR-AUD will be determined at the following nominal times: 0 (pre-dose) and at 1, 2, 4, 6, 8, 24, and 72 hours post-dose on days 1, 29, 57 (exception: no 72-hour PK sample is required on Day 57). A single sample will be collected on Days 1, 14, 42, 70, and 168 along with the ADA samples. These single PK concentrations maybe used for deriving the PK parameters, if the concentrations are detectable.

Derivation of PK parameters will be the responsibility of CPMS group, [REDACTED].

If calculable, the following PK parameters listed in [Table 3-2](#) will be determined for DCR-AUD in plasma following single subcutaneous (SC) dose administration.

Table 3-2 Plasma Pharmacokinetic Parameters After Each Dose Administration of Multiple Dose Study

Parameter	WNL Name	CDISC Name	Definition
C _{max}	Cmax	CMAX	Maximum observed concentration
C _{last}	Clast	CLST	Last measurable concentration
C _{min}	Cmin	CMIN	Minimum observed concentration in a dosing interval after last dose administration
t _{max}	Tmax	TMAX	Time corresponding to occurrence of C _{max}
t _½	HL_Lambda_z	LAMZHL	Apparent terminal elimination half-life
λ _z	Lambda_z	LAMZ	Terminal elimination rate constant
AUC _{0-last}	AUClast	AUCLST	Observed AUC from time zero to the last quantifiable concentration
AUC _{0-t}	AUCT	AUCINT(0-X)	Observed AUC from time zero to some fixed time t (i.e., AUC ₂₄ or AUC ₄₈)
AUC _{0-inf}	AUCINF_obs	AUCIFO	AUC from time zero extrapolated to infinity
%AUC _{ex}	AUC_%Extrap_obs	AUCPEO	Percentage of AUC _{0-inf} obtained by extrapolation beyond t _{last}

Parameter	WNL Name	CDISC Name	Definition
CL/F	Cl_F_obs	CLFO	Apparent clearance following SC administration
V _z /F	Vz_F_obs	VZFO	Apparent volume of distribution during terminal phase

Source: NCI EVS Terminology Resources website:
<http://www.cancer.gov/cancertopics/cancerlibrary/terminologyresources/cdisc>.

Approved

4 STATISTICAL METHODS

4.1 Data Quality Assurance

All tables, figures, and data listings to be included in the report will be independently checked for consistency, integrity, and in accordance with standard [REDACTED] procedures.

4.2 General Presentation Considerations

This section is not applicable to PK data.

4.2.1 Treatment

480 mg of DCR-AUD and placebo in each arm.

4.2.2 Study Day

Study days will be numbered relative to the first day of study drug administration.

- If the date of event is before the study drug administration, then:

Study day = (Date of measurement – Date of study drug administration [i.e. Day 1])

- If the date of event is on or after the study drug administration, then:

Study day = (Date of measurement – Date of study drug administration [i.e. Day 1]) + 1

